6 STUDY PROCEDURES

6.1 Schedule of Study Procedures

The schedule of study procedures/assessments are summarized in [Table 1](#) for Part A and [Table 2](#) for Part C of the study. Study procedures listed in each row of the table should be performed at the visits designated in each column where an “X” is marked, and as indicated in the footnote, where applicable. Further information related to each study procedure type are described in Section [6.3.3](#).

The calendar day of the first study drug administration is designated as Day 1; subsequent calendar days are Days 2, 3, etc. Note that each part of the study (Parts A and C) has their own unique numbering of calendar days.

Written informed consent must be obtained prior to performing any protocol specific procedures. After providing full informed consent, subjects will undergo a medical screen to determine their eligibility for participation based on the criteria outlined in this protocol. Part C, which is an optional long-term extension study will require subjects to sign a separate informed consent form from that in Part A.

The site should make every effort to perform procedures at the scheduled times, and the actual time should be recorded in the source documents and on the case report forms.

Acceptable deviations from the timing of assessments are as follows:

- Day 8 through Day 29: \pm 3 days
- Day 57 through Day 169: \pm 7 days

Additional safety tests, such as vital signs (BP, heart rate, respiratory rate, and body temperature), physical exams, ECGs, and laboratory safety tests, may be obtained during the course of the study on the basis of newly available data to ensure appropriate safety monitoring.

In Part C, in cases where the subject is unable to return to the clinic for a clinic visit for reasons due to significant physical or geographic limitations, or at the Investigator’s discretion, a protocol-trained nurse may be sent to the subject’s home and the study visit procedures performed in the subject’s home. The only exception to this is for the day 29 visit of Part C which must be done at the research center.

6.2 Total Blood Volume

The total volume of blood to be drawn from each subject for safety, PK, and PD laboratory assessments is approximately [REDACTED]

Additional safety laboratory tests may be drawn as needed to manage any emergent health needs as directed by the Investigator.

6.3 Description of Study Procedures / Assessments

6.3.1 Informed consent

Written informed consent using an IRB-approved informed consent form must be obtained prior to performing any protocol specific procedures. Within 30 days after providing full informed consent, subjects will undergo a medical screen to determine their eligibility for participation based on the criteria outlined in this protocol. Part C, which is an optional long-term extension study will require subjects to sign a separate informed consent form from that in Part A.

6.3.2 Overnight Residency, Standardized Meals, and Restrictions

Subjects will be admitted and remain resident in the clinical research center (CRC) beginning Day -2 through the morning of Day 6 in Part A, and Day -2 through the morning of Day 2 for Part C.

[REDACTED]

[REDACTED]

[REDACTED]

[REDACTED]

[REDACTED]

Should there be a clinically significant change between Screening and Day 1 of either Part A or Part C such that subjects no longer meet the eligibility criteria, they will no longer be eligible for the study and should be listed as a screen failure.

6.3.3 Inclusion and Exclusion Criteria

Section 4 provides a listing of inclusion criteria which subjects must meet to be eligible. Any subjects meeting exclusion criteria should not be enrolled in the study.

6.3.4 Medication and Medical History

Complete medication record and medical history at the pretreatment screening evaluation will include evaluation and therapies for past and present cardiovascular, respiratory, gastrointestinal, renal, hepatic, neurological, endocrine, lymphatic, hematologic, immunologic, dermatologic, psychiatric, genitourinary, substance abuse, surgical history, or any other diseases or disorders. If any worsening in severity or frequency occurs for an existing condition or a new event occurs after signing of the informed consent, this must be recorded as an AE. Prior to initiating Part C, the medication and medical history should be reevaluated and updated accordingly. Any events occurring < 30 days since the last dose of study drug in part A (or Part B) should be recorded as an AE. Any event that occurs \geq 30 days since the last dose of study drug in Part A (or Part B) but prior to Part C should be recorded as medical history (unless the Investigator deems the event related to prior study drug use).

6.3.5 Body Height, Weight and BMI

Body height and weight will be measured at the time points described in [Table 1](#) for Part A and [Table 2](#) for Part C. Care will be taken to ensure the measurements for weight occur at approximately the same time each day (\pm 15 minutes) using the same scale and without clothing (or where necessary with the same light clothing). BMI will be automatically calculated in the EDC system once weight and height are entered.

6.3.6 Temperature and Respiratory Rate

Temperature and respiratory rate are to be measured at the time points described in Table 1 for Part A.

Temperature is to be measured at time points described in Table 2 for Part C.

6.3.7 Orthostatic Standing Test

The orthostatic standing test (including supine blood pressures) will be performed at the time points listed in Table 1 for Part A and Table 2 for Part C and according to the details provided in the footnotes of each table.

At each time point, BP and HR measurements will be recorded with automated (or manual) sphygmomanometer while supine at 5 and 10 min (with the torso and head elevated 30 degrees from horizontal), after seated at 5 and 10 min and after 1, 3, 5, and 10 min while

standing. The standing time will be measured with a chronometer and the duration of standing will be recorded. The total duration of standing may occur in between the timepoints (ie, 1, 3, 5, and 10 minutes) for the standing test, or the subject may be able to stand for longer than the 10-minute standing test. In either case, the total duration should be recorded. More details related to the sequence of dosing and orthostatic assessments are described in [Table 1](#) for Part A and [Table 2](#) for Part C.

Blood pressure and HR collected after 10 minutes supine and seated from the orthostatic standing test will be used for safety vital sign assessment.

6.3.8 Supine Blood Pressure

Supine blood pressure will be measured at specified time points in the Schedule of Procedures / Assessments Table 1 for Part A and [Table 2](#) for Part C.

In Part C, on Days 8, 22, 57 and 113, supine blood pressures will be collected twice in the morning before eating (after 5 and 10 minutes resting at 30° elevation), and twice again at least 4 hours after dosing (but no more than 7 hours and before lunch) after 5 and 10 minutes resting at 30° head and torso elevation (Table 2). On Day -2, supine blood pressures should be measured after 5 and 10 minutes resting at 30° head and torso elevation.

6.3.9 Autonomic Function Testing

Where appropriate, autonomic function testing will be conducted to confirm the diagnosis of autonomic dysfunction and will include the following assessments. Note that the results of this testing will be recorded in the subject source notes but will not be collected in the case report form.

- HR will be monitored by ECG and BP continuously with tonometry or finger plethysmography and intermittently with an oscillometric device. These tests include sinus arrhythmia and Valsalva maneuver.
- Deep breathing-vagally-mediated sinus arrhythmia (SA) is assessed during controlled breathing (pattern of 5 seconds inhalation and 5 seconds exhalation repeated over 90 seconds).

- Valsalva maneuver. The subject will exhale against a 40 mm Hg pressure. Changes in intrathoracic pressure produce autonomically modulated transient changes in HR and BP.

6.3.10 24-Hour Blood Pressure Monitoring

In Part C, at sites where ambulatory blood pressure monitoring equipment is available, on Day -1, beginning approximately 24 hours before dosing on Day 1, ambulatory blood pressure monitoring equipment will be attached to the subject and blood pressure monitored during the 24 hour period before dosing. In addition, approximately 72 to 48 hours before the subject returns to the clinic for the Day 15, Day 29, Day 85 and Day 169 visits, subjects will put on the 24 hour blood pressure monitoring equipment and initiate the recording.

Once the 24 hour session is complete subjects will remove and return the equipment to the research center during the next visit. During each 24 hour session, the blood pressure monitoring device will be programmed to automatically measure blood pressure every 2 hours beginning after the monitoring device is powered on. In addition, subjects should be instructed to manually initiate 2 recordings to occur approximately 30 and 20 minutes before eating each morning after sitting supine (30 degree elevation) for at least 10 minutes.

During each 24-hour session subjects should also maintain a log of their posture at the time of each blood pressure measurement. For sites where ambulatory equipment are not available, desk top blood pressure devices may be used and provided to the subject for home use. Subjects will be instructed to measure and record blood pressure on the days and time points described above and in [Table 2](#). More details regarding the ambulatory monitoring will be provided in a separate manual.

6.3.11 Electrocardiogram

At time points specified in the Schedule of Study Procedures / Assessments ([Table 1](#) for Part A and Table 2 for Part C) subject will have a 12-lead ECG following a 10 minute rest period. QTc corrections will be made using the Fredericia correction formula.

6.3.12 Physical Examination

The physical examinations at the pretreatment screening visit for Part A and the Day -1 visit for Part C will be performed by an appropriately qualified individual (eg, physician, nurse practitioner, physician's assistant or equivalent under the supervision of a physician), and will include examination of the following: general appearance; head, ears, eyes, nose, and

throat; neck, skin; cardiovascular system; respiratory system; abdominal system; lymphatic system, dermatologic system, musculoskeletal system, and nervous system. Subsequent physical examinations after the screening visit for Part A and the Day -1 visit for Part C can be abbreviated and symptomatic, largely focused on evaluation of AEs, if any, and any abnormalities identified on the screening (Part A)/Day -1 (Part C) examination.

6.3.13 Pregnancy Test

For female subjects of child bearing potential, serum beta-human chorionic gonadotropin pregnancy tests will be conducted at the screening visit in Part A.

For Part C, a urine pregnancy test will be conducted at the Day -2 visit. If the urine pregnancy test is positive, a serum pregnancy test will be done to confirm the result.

Pregnancy tests must be negative for a subject to participate in the study.

6.3.14 Laboratory Tests

Blood (for hematology and serum chemistry) and urine (for urinalysis) should be sent to the local or central laboratory according to the schedule of procedures/assessments in [Table 1](#) for Part A and [Table 2](#) for Part C.

6.3.14.1 Hematology

Hematology analytes to be tested include the following: hematocrit; hemoglobin; white blood cell count (WBC), including differential count by microscopy with percentage of immature neutrophils (bands), mature neutrophils, and eosinophils; and platelet count.

6.3.14.2 Serum Chemistry

Serum chemistry analytes to be tested include the following: potassium, magnesium, blood urea nitrogen (BUN), creatinine, C-reactive protein, creatine kinase, albumin, total bilirubin, alkaline phosphatase, lactate dehydrogenase (LDH), alanine aminotransferase (ALT), and aspartate aminotransferase (AST).

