1.4 Risks and Benefits

[REDACTED] suggesting that TD-9855 has the potential to provide a novel treatment option for nOH.

While it is not known whether TD-9855 will provide clinical efficacy, this study will provide a number of beneficial services to subjects. These include autonomic evaluations, neurohumoral evaluation and information on new research developments in the field. Subjects will have access to routine autonomic follow up that may improve orthostatic symptoms. They will have symptom rating testing performed that may assist in educational planning.

During the conduct of the TD-9855 clinical development program, the following have been recognized as important potential risks, with none characterized as identified risks associated with the administration of TD 9855:

- Increase in heart rate
- Increase in BP
- Syncope

Possible risks to subjects participating in this study include adverse events associated with other SNRIs, such as nausea, dry mouth, headache, dizziness, somnolence, fatigue, diarrhea, insomnia, vomiting, syncope, seizures, constipation, hyponatremia, hyperhidrosis, urinary retention, and decrease appetite.

Furthermore, subjects may experience adverse effects as a result of study procedures, such as repeated blood sampling and associated procedures.

To help ensure subject safety, subjects will be closely monitored during this study. The study will be conducted in the Clinical and Translational Science Awards Centers (CTSAs) of the respective participating institutions comprising the Autonomic Disorders Consortium whenever possible. When a CTSA is not available, study visits will be conducted in the Investigator's autonomic disorders clinic or appropriately qualified research facility. The schedule of procedures conducted during the open-label out-patient extension requires subjects to return to the clinic on a regular basis during the dosing and follow up periods and participate in telephone based evaluations on a weekly basis. If subjects are unable to return to the clinic as indicated by the schedule of procedures, home visits will be conducted by protocol-trained nurses. If any participant should incur any unexpected and untoward event during the testing procedure, the emergency caregivers (cardiologists, anesthesiologists, social workers, and psychologists) would become available on an immediate basis to provide necessary emergent management.

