6.3.14.3 Urinalysis

Urinalysis analytes to be tested include the following: presence of blood, bilirubin, urobilinogen, nitrite, leukocytes, and (if dipstick positive) microscopic examination of sediment (sediment results will not be collected in the case report form).

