9.3.6 Clinical Laboratory Results

The study used a mixture of local and central labs, lab units, normal ranges will be converted using the Standard International lab unit if possible. Lab data will be counted as Low, Normal, and High for each visit by applying the local lab normal ranges. Lab shift tables from baseline to discharge/follow-up will be summarized.

Clinical laboratory test results will be listed by subject. Reference ranges provided by the laboratory for each parameter will be used to evaluate the clinical significance of laboratory test results. Values falling outside of the relevant reference range will be flagged, as appropriate, in the data listings. Abnormalities in clinical laboratory test results will be listed in a separate listing.

Cumulative urine volume over the 24-hour period for each dosing day will be summarized by Study Day and dose.

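### Hyponatremia is listed as a possible risk, but none of the five scheduled chemistry panels is required to include sodium

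*Protocol*

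**What the plan says.** Protocol Section 1.4 has two risk lists. The first gives three important potential risks recognized in the TD-9855 program (increased heart rate, increased blood pressure, syncope), none of them characterized as an identified risk. The second opens with "Possible risks to subjects participating in this study include adverse events associated with other SNRIs" and ends with "hyponatremia, hyperhidrosis, urinary retention, and decrease appetite".

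Protocol Section 6.3.14.2 sets the chemistry panel: "Serum chemistry analytes to be tested include the following: potassium, magnesium, blood urea nitrogen (BUN), creatinine, C-reactive protein, creatine kinase, albumin, total bilirubin, alkaline phosphatase", followed by LDH, ALT and AST. The electrolytes are potassium and magnesium.

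Protocol Table 1 schedules chemistry at Screening, Day -1 and Discharge. Table 2 marks safety labs under Day -2 (footnote o allows Day -2 or Day -1) and Day 169, and nowhere between. Footnote m puts the last dose on Day 140.

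SAP Section 9.3.6 adds no analyte. For reporting it says "Lab shift tables from baseline to discharge/follow-up will be summarized". The SAP introduction limits that document to Part C.

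**The concern.** Most of the events in the second list of Section 1.4 reach the case report form because the subject describes them or the site observes them. Hyponatremia is different: it is defined by a laboratory value, so it is found only if sodium is measured. A site that follows the protocol exactly need never measure it.

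What is at stake is how the safety data can be read. The laboratory listings and shift tables need not contain any sodium result. If the study report then recorded no hyponatremia, that statement would say little, because the plan did not require anyone to look.

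**Working it through.** The documents give no figure to reproduce. The check sets the panel, the schedule and the risk list side by side.

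**1. Is sodium on any required list?**

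| Source | Content | Sodium |
|---|---|---|
| Protocol 6.3.14.2, chemistry | Potassium, magnesium, BUN, creatinine, CRP, CK, albumin, total bilirubin, ALP, LDH, ALT, AST (12) | No |
| Protocol 6.3.14.1, hematology | "Hematology analytes to be tested include the following: hematocrit; hemoglobin; white blood cell count (WBC"), differential, platelets | No |
| Protocol 6.3.14.3, urinalysis | "presence of blood, bilirubin, urobilinogen, nitrite, leukocytes", and sediment if dipstick positive | No |
| PK and PD samples, Tables 1 and 2 | TD-9855, NE, DHPG | No |
| SAP 9.3.6 | No analyte list | No |

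Section 6.3.14.2 shows no redaction, so the gap is not a result of blacked-out text.

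**2. How many scheduled panels are affected?** Part A has 3 (Screening, Day -1, Discharge). Part C has 2 (Day -2 or -1, and Day 169). 3 + 2 = 5, and none is required to include sodium.

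**3. What would adding sodium to those five panels yield?**

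- Part A before dosing: Screening and Day -1.
- Part A on drug: Discharge only. Day 1 is placebo and active dosing runs from Day 2 to Day 5 at the latest, so the maximum is 5 - 2 + 1 = 4 active doses. Table 1 allows discharge as early as Day 3, which would follow a single active dose on Day 2.
- Part C before dosing: Day -2 or -1.
- Part C after baseline: Day 169 only. 169 - 140 = 29 days after the last dose.

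**4. Does the visit window change the Part C result?** Section 6.1 allows ±7 days from Day 57 through Day 169. Assume the last dose moves with the Day 140 visit. The shortest gap is then (169 - 7) - (140 + 7) = 162 - 147 = 15 days, and the longest is (169 + 7) - (140 - 7) = 176 - 133 = 43 days. Subjects who stop early have follow-up visits 2 and 4 weeks after their final dose, so those values are off drug too. As extracted, the Table 2 dosing row also appears to carry a mark under Day 155. Footnote m is explicit about Day 140, and even on the other reading the gap is 169 - 155 = 14 days. On every reading, up to 20 weeks of daily dosing has no scheduled on-treatment chemistry.

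**5. Where would the values be reported?** The SAP's list of outputs, including shift Tables 14.3.10.1 and 14.3.10.2, is for Part C only. Those tables would compare a Part C baseline with a Day 169 value. The Part A discharge value, the only on-drug one, would be summarized under protocol Section 8.3.9.

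**The case against.** The strongest reply has three parts.

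- **The risk is remote.** Hyponatremia appears only among 16 events attributed to other SNRIs, not among the three important potential risks of TD-9855, and the documents give no incidence for it. This stands. It lowers the weight of the point, and the item should be described as a risk of related drugs, not as a recognized risk of TD-9855.
- **The list may be a minimum.** The panel is introduced with the word for inclusion, samples go to a local or central laboratory (Section 6.3.14), and a laboratory may report sodium anyway. This stands as a possibility, but what is collected would then vary by site and nothing makes it a requirement.
- **Other routes exist.** Section 6.1 allows additional laboratory safety tests, and Section 6.2 allows further draws for emergent health needs. Exclusion 21 lets the investigator act on any laboratory result. Section 6.3.2 removes subjects whose eligibility changes before Day 1 of either part. These routes are real but discretionary, and none names sodium.

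Because of these routes, a reader who infers that hyponatremia cannot be detected, or that no Part A abnormality could bear on entry to Part C, goes further than the documents allow. What they support is that no scheduled panel is required to find it.

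**Conclusion.** The gap is real and modest. A possible risk that only a laboratory value can establish is matched by no required measurement on any of the five scheduled panels. This rests on the readable text of both documents and on taking Section 6.3.14.2 as the full required panel.

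Three further readings are tempting and should not be drawn:

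- That early hyponatremia would be mistaken for OHSA symptoms. Neither document says so.
- That the gap can be expressed as a detection rate. The documents give no case rate, so a percentage would only restate that the analyte is missing.
- That one added word settles the matter and the SAP tables then carry the result. In Part C the added analyte would still produce no on-treatment value, and the SAP tables would not show the Part A discharge value.

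The shortage of on-treatment safety labs in Part C applies to every chemistry analyte. It matters here because it limits what the simple fix can deliver.

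**What to change.** 1. Add sodium to the analyte list in protocol Section 6.3.14.2 for all chemistry panels already scheduled in Tables 1 and 2. Cost: one more analyte on serum already drawn, with no added visit or blood draw.
2. State that the Part A sodium values, including the discharge value, are summarized under protocol Section 8.3.9, since the supplied SAP covers Part C only.
3. Reconcile the Table 2 safety-lab row with Section 1.4. Either schedule chemistry during Part C treatment or state why a single post-baseline panel on Day 169 is considered sufficient. The choice is the sponsor's. Footnote i of Table 2 already has blood taken for PK at the Day 29 and Day 85 clinic visits, so an on-treatment panel at either would add a sample and an assay but no visit.
4. If sodium is not added, the study report should say that it was not a scheduled measurement, so that an absence of reported hyponatremia is not read as evidence against it.

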6.3.14.3 Urinalysis

Urinalysis analytes to be tested include the following: presence of blood, bilirubin, urobilinogen, nitrite, leukocytes, and (if dipstick positive) microscopic examination of sediment (sediment results will not be collected in the case report form).

6.3.14.4 Urine Drug Screen

At screening a urine drug screen for drugs of abuse will be performed.

